#### 12.1.4 Response Criteria

##### 12.1.4.1 Evaluation of Target Lesions

**Complete Response (CR):** Disappearance of all target lesions. Any pathological lymph nodes

(whether target or non-target) must have reduction in short axis to <10 mm (<1 cm).

Partial Response (PR): At least a 30% decrease in the sum of the diameters of target lesions, taking as reference the baseline sum diameters.

Progressive Disease (PD): At least a 20% increase in the sum of the diameters of target lesions, taking as reference the smallest sum on study (this includes the baseline sum if that is the smallest on study). In addition to the relative increase of 20%, the sum must also demonstrate an absolute increase of at least 5 mm (0.5 cm). (Note: the appearance of one or more new lesions is also considered progressions).

Stable Disease (SD): Neither sufficient shrinkage to qualify for PR nor sufficient increase to qualify for PD, taking as reference the smallest sum diameters while on study.

#### 12.1.4.2 Evaluation of Non-Target Lesions

Complete Response (CR): Disappearance of all non-target lesions and normalization of tumor marker level. All lymph nodes must be non-pathological in size (<10 mm [<1 cm] short axis).

Note: If tumor markers are initially above the upper normal limit, they must normalize for a patient to be considered in complete clinical response.

Non-CR/Non-PD: Persistence of one or more non-target lesion(s) and/or maintenance of tumor marker level above the normal limits.

Progressive Disease (PD): Appearance of one or more new lesions and/or *unequivocal progression* of existing non-target lesions. *Unequivocal progression* should not normally trump target lesion status. It must be representative of overall disease status change, not a single lesion increase.

Although a clear progression of “non-target” lesions only is exceptional, the opinion of the treating physician should prevail in such circumstances, and the progression status should be confirmed at a later time by the review panel (or Principal Investigator).

#### 12.1.4.3 Evaluation of Best Overall Response

The best overall response is the best response recorded from the start of the treatment until disease progression/recurrence (taking as reference for progressive disease the smallest measurements recorded since the treatment started). The patient's best response assignment will depend on the achievement of both measurement and confirmation criteria.

**For Patients with Measurable Disease (i.e., Target Disease)**

| Target Lesions | Non-Target Lesions          | New Lesions | Overall Response | Best Overall Response when Confirmation is Required* |
|----------------|-----------------------------|-------------|------------------|--|
| CR             | CR                          | No          | CR               | ≥4 wks. Confirmation**                               |
| CR             | Non-CR/Non-PD               | No          | PR               | ≥4 wks. Confirmation**                               |
| CR             | Not evaluated               | No          | PR               |  |
| PR             | Non-CR/Non-PD/not evaluated | No          | PR               | Documented at least once ≥4 wks. from baseline**     |
| SD             | Non-CR/Non-PD/not evaluated | No          | SD               |  |
| PD             | Any                         | Yes or No   | PD               | no prior SD, PR or CR                                |
| Any            | PD***                       | Yes or No   | PD               |  |
| Any            | Any                         | Yes         | PD               |  |

\* See RECIST 1.1 manuscript for further details on what is evidence of a new lesion.  
 \*\* Only for non-randomized trials with response as primary endpoint.  
 \*\*\* In exceptional circumstances, unequivocal progression in non-target lesions may be accepted as disease progression.

Note: Patients with a global deterioration of health status requiring discontinuation of treatment without objective evidence of disease progression at that time should be reported as “*symptomatic deterioration*.” Every effort should be made to document the objective progression even after discontinuation of treatment.

**For Patients with Non-Measurable Disease (i.e., Non-Target Disease)**

| Non-Target Lesions | New Lesions | Overall Response |
|--------------------|-------------|------------------|
| CR                 | No          | CR               |
| Non-CR/non-PD      | No          | Non-CR/non-PD*   |
| Not all evaluated  | No          | not evaluated    |
| Unequivocal PD     | Yes or No   | PD               |
| Any                | Yes         | PD               |

\* ‘Non-CR/non-PD’ is preferred over ‘stable disease’ for non-target disease since SD is increasingly used as an endpoint for assessment of efficacy in some trials so to assign this category when no lesions can be measured is not advised

**12.1.5 Duration of Response**

Duration of overall response: The duration of overall response is measured from the time measurement criteria are met for CR or PR (whichever is first recorded) until the first date that recurrent or progressive disease is objectively documented (taking as reference for progressive disease the smallest measurements recorded since the treatment started) or until death.

The duration of overall CR is measured from the time measurement criteria are first met for CR until the first date that progressive disease is objectively documented.

Duration of stable disease: Stable disease is measured from the start of the treatment until the criteria for progression are met, taking as reference the smallest measurements recorded since the treatment started, including the baseline measurements.

#### 12.1.6 Progression-Free Survival – Co-Primary Endpoint

PFS is defined as the duration of time from date of randomization to time of progression or death (whichever occurs first). This analysis is intent-to-treat including all randomized patients. Patients who come off of study treatment for clinical progression without radiographic progression (i.e. clinical progression) will be coded as progression for the analysis and the date of clinical progression is the time of progression. Due to the rapid progression of the disease in the majority of patients, little loss to follow up is expected, but subjects who are lost to follow-up as of the data analysis cutoff date will be right-censored. The censoring date will be determined from the date the subject was last evaluated for progression. PFS within each treatment arm will be summarized descriptively using Kaplan-Meier plots, and compared between arms using log-rank tests.

Note: For participants who receive treatment beyond disease progression PFS will be dated as follows:

- For patients who have progressive disease on two sequential scans, the date of progression will be backdated to the time of first progression.
- For patients who do not have progressive disease on the scan after progressive disease was first documented, the date of progression will be dated to the time that a second scan shows progression.

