### 6.2 Continuation after Unconfirmed Progression

The study regimens in this trial trigger immune-mediated responses, which require activation of the immune system prior to the observation of clinical responses. Patients may continue receiving their assigned treatment if their disease progresses based on RECIST 1.1 criteria if 1) the patient is clinically stable; 2) No symptoms or signs indicating disease progression, including clinically significant laboratory values; 3) the patient is informed of their scan results and agrees to continue therapy, and 4) the patient provider agrees that remaining on study would be appropriate for the patient. If the following scan after first noted progression confirms progressive disease by RECIST 1.1, the scan where progression was first noted will be used to calculate PFS.

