## 9. STATISTICAL CONSIDERATIONS

### 9.1 Study Design/Endpoints

The proposed study is an open-label, randomized phase 2 trial evaluating atezolizumab in combination with CDX-1127 (varlilumab) with or without the addition of cobimetinib in unresectable, pre-treated cholangiocarcinoma. Patients will be randomized in a 1:1 ratio to the two arms. The primary objective of the trial is to determine whether the combination of checkpoint blockade with an immune co-stimulatory yields a clinically compelling antitumor activity (measured as overall response rates [ORR, assessed by RECIST 1.1] and progression free survival [PFS, assessed by RECIST 1.1]) and if this effect can be further amplified with the addition of MEK inhibition. Secondary endpoints include safety, overall survival (OS), immunologic correlates, and pharmacokinetics of atezolizumab and varlilumab. Objective response (OR) and PFS are co-primary endpoints.

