##### Progression Free Survival (PFS):

PFS is defined as the duration of time from date of randomization to time of progression or death. This analysis is intent-to-treat including all randomized patients. Patients who come off of study treatment for clinical progression without radiographic progression (i.e. clinical progression) will be coded as progression for the analysis, and the date of progression is the date of clinical progression. Due to the rapid progression of the disease in the majority of patients, little loss to follow up is expected, but subjects who are lost to follow-up as of the data analysis cutoff date will be right-censored. The censoring date will be determined from the date the subject was last evaluated for progression. PFS within each treatment arm will be summarized descriptively using Kaplan-Meier plots, and compared between arms using log-rank tests.

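### The note in 12.1.6 sets aside an unconfirmed first RECIST 1.1 progression only for patients kept on treatment, so the co-primary PFS date depends on a decision made with the arm known

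*Combined protocol and SAP*

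**What the plan says.** - **Design and endpoint (9.1).** "The proposed study is an open-label, randomized phase 2 trial", with co-primary "progression free survival [PFS, assessed by RECIST 1.1". The PFS paragraph reads "PFS is defined as the duration of time from date of randomization to time of progression or death". It covers all randomised patients and codes clinical progression as an event. It has no rule for treatment beyond progression.
- **Progression criterion (12.1.4.1).** "At least a 20% increase in the sum of the diameters of target lesions", measured from the smallest sum on study and with a 5 mm absolute increase. A new lesion also counts. No confirming scan is required.
- **Continuation (6.2).** After a RECIST 1.1 progression, treatment may continue if the patient is clinically stable, has no symptoms or signs of progression, is told of the result and agrees, and if "the patient provider agrees that remaining on study would be appropriate for the patient". PFS is dated here only for the case in which the next scan confirms progression: "the scan where progression was first noted will be used to calculate PFS".
- **Dating note (12.1.6).** The section repeats the 9.1 definition and adds: "For participants who receive treatment beyond disease progression PFS will be dated as follows". Progression on two sequential scans is backdated to the first. If the next scan does not show progression, "the date of progression will be dated to the time that a second scan shows progression".
- **Test (9.2).** The arms are compared on PFS only if both meet the response criterion. The plan is 55 events for 90% power at HR 0.5, one-sided 0.10.
- **Scans (Section 11, note N).** Every 8 weeks. After treatment stops, this schedule continues only for patients who stopped for a reason other than progression.

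**The concern.** The stated endpoint and the progression criterion make the first RECIST 1.1 progression the event. The note changes that for one subset, defined after randomisation by whether treatment went on. The people who make that choice know the arm. I found no blinded review of progression for PFS; 12.1.4.2 mentions a review panel or the Principal Investigator only for progression confined to non-target lesions. I also found no planned analysis by first progression.

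The between-arm log-rank test is the only randomised comparison on a primary endpoint. If the arms differ in how often patients continue, or in how often a first progression goes unconfirmed, event times in one arm are lengthened more than in the other for reasons that need not reflect disease control.

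**Working it through.** **1. The same scan under the rule as written** (illustration on the 8-week schedule, first progression at week 8)

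| After week 8 | Week 16 | Later | PFS event |
|---|---|---|---|
| Taken off treatment | scan not required by note N | – | week 8 |
| Kept on | progression | – | week 8 (backdated) |
| Kept on | no progression | progression at week 24 | week 24 |
| Kept on | no progression | no further progression scan | clinical progression or death; otherwise censored at last assessment |

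Rows 1 and 3 start from the same scan and differ by at least 16 weeks: 16 × 7 / 30.4375 = 3.7 months, longer than the 3.5-month doublet median assumed in 9.2. Neither bullet of the note covers a patient who is treated past a first progression and has no further scan.

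**2. The plan's own figure.** Schoenfeld, 1:1 allocation, one-sided 0.10, 90% power, HR 0.5: events = 4 × (1.2816 + 1.2816)² / (ln 0.5)² = 26.28 / 0.4805 = 54.7, so 55. Power at 55 events is 0.901. The stated 55 events and 90% reproduce.

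**3. Error with no true difference.** Common inputs from the documents: 32 per arm, median 3.5 months in both arms, scans every 8 weeks, 4 patients a month (16 months for 64), one-sided 0.10 log-rank. Added assumptions: exponential PFS, 20% of events are deaths, and each re-dated progression moves by 16 weeks. The re-dating shares are also assumed; the documents give none. With 3,000 trials per setting the simulation standard error near 0.10 is √(0.1 × 0.9 / 3000) = 0.005.

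| Re-dated, triplet/doublet | Analysis at 24 months | Analysis at 55 events |
|---|---|---|
| 0%/0% | 0.098 | 0.108 |
| 10%/0% | 0.157 | 0.15 and 0.165 (two runs) |
| 20%/0% | 0.236 | 0.204 |
| 20%/10% | 0.145 | – |
| 20%/20% | 0.104 | 0.109 |
| 0%/10% | – | 0.068 |
| 10%/20% | – | 0.059 |

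**4. The same question by continuation and non-confirmation.** A second model, with 4,000 trials per setting, analysis at 55 events and no separate deaths, sets the share of patients continued in each arm and the share u of first progressions that the next scan does not confirm.

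| Continued, triplet/doublet | u = 0.1 | u = 0.2 | u = 0.3 |
|---|---|---|---|
| 50%/50% | 0.095 | 0.094 | 0.100 |
| 60%/30% | 0.138 | 0.176 | 0.208 |
| 30%/60% | 0.076 | 0.056 | 0.042 |

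At medians of 7 and 3.5 months and u = 0.2, power is 0.875 (50%/50%), 0.953 (80%/20%) and 0.728 (20%/80%). With first-progression dating for everyone, error is 0.099 and power 0.887.

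**5. When the test is reached.** Under the 9.2 design (18 then 14 patients, at least 4 responses in 32), one arm passes with probability 0.072 at a true response rate of 5% and 0.901 at 20%. Both arms pass, if independent, with probability 0.072² = 0.005 and 0.901² = 0.81.

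**The case against.** The rule is written in advance, has an immunotherapy rationale in 6.2, and adds to the 9.1 definition a case which that section does not mention. On this view the defect is a missing cross-reference, and choosing confirmed over first progression is a matter of design preference. Part of this stands: the rule is pre-specified and the choice of convention is open. But this note is not a confirmation rule for all patients. It applies only to those kept on treatment, and a cross-reference would not remove that dependence.

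The proposed change is also partial. Clinical progression stays an event and is judged by staff who know the arm. That is true, but the change still removes the one element tied to continuation.

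A reader might infer more than the documents support:
- *That the rule favours the triplet.* Nothing shows this. Cobimetinib toxicity could lower continuation in the triplet arm and make the test conservative.
- *That continuing treatment by itself moves the date.* It does not. The next scan must also fail to show progression, and continuation needs clinical stability and patient agreement as well as the provider's.
- *That a first progression not seen again leaves the patient without an event.* Later death or clinical progression still counts.
- *That PFS is the only randomised comparison.* Section 9.4 also compares CD8+ change between arms.

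**Conclusion.** The point holds as a fault in the definition of a co-primary endpoint: identical scans can give different event dates according to a post-randomisation decision made with the arm known, in an analysis described as intent-to-treat. The RECIST 1.1 label for PFS comes from 9.1; 9.2 names no progression criterion.

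The size is conditional. Ten percentage points more re-dating in the triplet takes the nominal 0.10 error to about 0.16. The same gap in the other direction (0%/10%) takes it to about 0.07. Equal shares leave it near 0.10. These figures rest on assumed shares and exponential PFS, and apply only when the response criterion is met in both arms. Material bias is possible but not shown. The correction is worth making because it is cheap and because the PFS definitions in 9.1 and 12.1.6 should agree before analysis.

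**What to change.** In 9.1 and 12.1.6, define primary PFS as the time from randomisation to the earliest of first RECIST 1.1 progression, clinical progression as already defined, or death, for every randomised patient whether or not treatment continues. Keep the 12.1.6 re-dating as a named sensitivity analysis, and state in it how a patient with no scan after the first progression is handled. Align the PFS dating sentence in 6.2. The treatment rules in 6.2 do not change.

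The cost is wording. Both versions use data already collected, and the 55 events and sample size stand. The downside is a slightly shorter PFS if true pseudo-progression occurs, which the sensitivity analysis would show.

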#### 12.1.7 Overall Response Rate – Co-Primary Endpoint

The objective response rate defined as the proportion of response evaluable subjects who have a complete response (CR) or partial response (PR) using RECIST 1.1 criteria at any time during the study. The evaluable population includes all subjects who initiated therapy. Patient who have not received a follow-up scan, and thus are not evaluable for response, will be counted as non-responders.

### **12.2 Other Response Parameters**

#### 12.2.1 Overall Survival (OS)

OS is defined as the duration of time from date of randomization to time of death

## **13. STUDY OVERSIGHT AND DATA REPORTING / REGULATORY REQUIREMENTS**

Adverse event lists, guidelines, and instructions for AE reporting can be found in Section 10 (Adverse Events: List and Reporting Requirements).

### **13.1 Study Oversight**

This protocol is monitored at several levels, as described in this section. The Protocol Principal Investigator is responsible for monitoring the conduct and progress of the clinical trial, including the ongoing review of accrual, patient-specific clinical and laboratory data, and routine and serious adverse events; reporting of expedited adverse events; and accumulation of reported adverse events from other trials testing the same drug(s). The Protocol Principal Investigator and statistician have access to the data at all times through the CTMS web-based reporting portal.

All Study Investigators at participating sites who register/enroll patients on a given protocol are responsible for timely submission of data via Medidata Rave and timely reporting of adverse events for that particular study. This includes timely review of data collected on the electronic CRFs submitted via Medidata Rave.

All studies are also reviewed in accordance with the enrolling institution's data safety monitoring plan.

### **13.2 Data Reporting**

Medidata Rave is a clinical data management system being used for data collection for this trial/study. Access to the trial in Rave is controlled through the CTEP-IAM system and role assignments.

Requirements to access Rave via iMedidata:

- A valid account, and
- Assigned a Rave role on the LPO or PO roster at the enrolling site of: Rave CRA, Rave Read Only, Rave CRA (LabAdmin), Rave SLA, or Rave Investigator.

Rave role requirements:

- Rave CRA or Rave CRA (Lab Admin) role, must have a minimum of an Associate Plus (AP) registration type,
- Rave Investigator role, must be registered as an Non-Physician Investigator (NPIVR) or Investigator (IVR), and
- Rave Read Only role, site staff must have at a minimum an Associates (A) registration type.
- Refer to <https://ctep.cancer.gov/investigatorResources/default.htm> for registration types and documentation required.

If the study has a DTL, individuals requiring write access to Rave must also be assigned the appropriate Rave tasks on the DTL.

Upon initial site registration approval for the study in Regulatory Support System (RSS), all persons with Rave roles assigned on the appropriate roster will be sent a study invitation email from iMedidata. To accept the invitation, site staff must either click on the link in the email or log in to iMedidata via the CTSU members' website under *Data Management > Rave Home* and click to *accept* the invitation in the *Tasks* pane located in the upper right-corner of the iMedidata screen. Site staff will not be able to access the study in Rave until all required Medidata and study specific trainings are completed. Trainings will be in the form of electronic learnings (eLearnings) and can be accessed by clicking on the eLearning link in the *Tasks* pane located in the upper right corner of the iMedidata screen. If an eLearning is required for a study and has not yet been taken, the link to the eLearning will appear under the study name in the *Studies* pane located in the center of the iMedidata screen; once the successful completion of the eLearning has been recorded, access to the study in Rave will be granted, and a *Rave EDC* link will replace the eLearning link under the study name.

Site staff that have not previously activated their iMedidata/Rave account at the time of initial site registration approval for the study in RSS will receive a separate invitation from iMedidata to activate their account. Account activation instructions are located on the CTSU website in the Data Management section under the Rave resource materials (Medidata Account Activation and Study Invitation Acceptance). Additional information on iMedidata/Rave is available on the CTSU members' website in the Data Management > Rave section at [www.ctsu.org/RAVE/](http://www.ctsu.org/RAVE/) or by contacting the CTSU Help Desk at [name] or by e-mail at [[contact]](mailto:[contact]).

### 13.2.1 Method

This study will be monitored by the Clinical Trials Monitoring Service (CTMS). Data will be submitted to CTMS at least once every two weeks via Medidata Rave (or other modality if approved by CTEP). Information on CTMS reporting is available at:

<http://www.theradex.com/clinicalTechnologies/?National-Cancer-Institute-NCI-11>. On-site audits will be conducted on an 18-36 month basis as part of routine cancer center site visits. More frequent audits may be conducted if warranted by accrual or due to concerns regarding data quality or timely submission. For CTMS monitored studies, after users have activated their accounts, please contact the Theradex Help Desk at [contact] or by email at [[contact]](mailto:[contact]) for additional support with Rave and completion of CRFs.

